10.2.1 Analysis of Primary and Secondary Endpoints and Correlative Studies

We will compare OS and progression-free survival (PFS) between historical control and experimental treatment arms using the log-rank test (we will also collect PFS data via chart review for the historical control patients). For our correlative studies, we will use the independent-sample t test to compare mean mutation burden between patient samples treated with RT+temozolomide or RT+temozolomide+TTFields. We may perform the same comparison within a linear regression framework if the need arises to adjust for any potential confounders for the effect of TTFields in our correlative studies.

To investigate the influence of electric field and energy deposition in the tumor on outcomes, we will use the Wilcoxon rank sum test to compare the electric field and specific absorption ratio parameters between: responders and non-responders; subjects with progression-free survival \geq and $<$ 1 year; subjects with overall survival \geq and $<$ 2 years; and subjects with overall survival \geq and $<$ 1.5 years. We will estimate Pearson correlation coefficients to assess the correlation of OS and PFS with electric field or specific absorption ratio parameters.

We may stratify the patients by MGMT methylation status, extent of resection, or a combination of the two.

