5.5.1 Screening

- Patients with newly diagnosed high-risk Grade II or III astrocytoma must undergo maximal safe resection (biopsy alone may be eligible).
- Patients must undergo chemoradiotherapy: concomitant 75mg/m² daily temozolomide with 80% prescribed dose completed and RT with minimal RT dose of 40 Gy delivered.
- Within three weeks prior to beginning adjuvant temozolomide, all patients will undergo a Baseline contrast-enhanced MRI of the brain.
- Within two weeks prior to beginning adjuvant temozolomide, all patients will undergo the following assessments:
 - Medical History and demographics
 - Medication History
 - Steroid Dose (recorded)
 - MGMT methylation status (if feasible, required for stratification)
 - Tumor Tissue sample – verify availability of FFPE, pathology slides, and/or frozen sample(s)
 - RANO assessment
 - Complete physical examination
 - Neurological status and KPS
 - CBC with differential
 - Pregnancy test (urine or serum) – WOCBP only
 - Biochemistry panel (Electrolytes, creatinine, bilirubin, liver enzymes)
 - Quality of life questionnaires (EORTC QLQ-C30/BN20, and MMSE)

No study-specific procedures may be performed prior to obtaining informed consent. However, assessments performed according to standard of care, prior to consent, may be used to fulfill the screening requirement if they are part of the patient’s medical record within the specified timeframe.

See Section “Enrollment Documentation Requirements” for a complete list of patient enrollment documentation.

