9.1 Control Cohort Rationale

Identification of a homogeneous historical cohort for comparing the investigational device data to historical data is of critical importance to this study's design and scientific rigor. This historical and contemporaneous cohort will include patients completing radiation and chemotherapy treatment no earlier than January 1, 2016, when chemotherapy became the care standard in these tumor subtypes [16].

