10 STATISTICAL CONSIDERATIONS

10.1 Statistical Hypotheses

- Primary Efficacy Endpoint: overall survival (OS)

Control arm: the control arm will consist of both historical and contemporaneous control patients. Historical controls will consist of TERT mutation-only astrocytoma patients treated and followed by the participating sites between January 1, 2016 and May 20, 2019. As described above, these patients will have received standard treatment and would have met first tier inclusion/exclusion criteria for the study. Data for these patients will be collected via chart review. Contemporaneous controls will also consist of patients who qualify for the trial and receive standard treatment but decide not to proceed with the Optune experimental treatment because of personal preference. This personal preference must be non-medical in nature. Based on clinical experience, most commonly this non-medical patient personal preference preventing Optune use will be unwillingness to shave his/her head and/or unwillingness to wear a visible medical device on his/her head most of the day.

- N = 90 patients total in an expected mixture ranging between 80 historical controls and 10 contemporaneous controls to 60 historical controls and 30 contemporaneous controls.
- Assumed median survival = 22 months (based on Figure 3A in Eckel-Passow et al [12])
- Follow-up = up to 60 months for the historical controls, up to 60 months for the contemporaneous controls

Experimental treatment arm: TERT mutation-only astrocytoma patients who will receive standard treatment plus TFields therapy at one of 15 participating centers.

- N = 90 patients

- Assumed accrual rate = 2.5 patients/month accumulated over 15 centers
- Accrual period = 36 months
- Follow-up period after the end of accrual = 24 months
- Assumed survival time distribution = Weibull with accelerating hazard and proportional hazards

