10.2 Sample Size Determination

To assess sample size requirements for detecting an improvement in median overall survival (OS) in the experimental treatment arm relative to the historical control arm, we initially assumed 60 to 90 patients receiving standard treatment and follow-up between 1-2016 and 5-2019 would be available for chart review. We assumed that these historical control patients would have a maximum follow-up time of 60 months. For the experimental treatment, we assumed an accrual rate of 2.5 patients per month across 15 participating centers and an accrual period of 36 months, yielding an enrollment of 90 patients in the experimental arm. The patients in the experimental arm would be followed for an additional 24 months after the end of accrual. We considered improvements in median survival ranging from 4 to 8 months to be of clinical interest. We also assumed that survival times would follow a Weibull distribution with proportional hazards and an accelerating hazard function (shape parameter $k=2.0$, estimated from Figure 3A in Eckel-Passow et al [12]. We also considered a more slowly accelerating Weibull shape parameter of $k=1.8$. Under these assumptions, the power to detect **improvements** in median OS using a one-sided log-rank test (one-sided $\alpha=0.05$) are summarized in Table 10 for selected combinations of historical control sample size, Weibull shape parameter, and number of months improvement in median OS [detectable effect size methodology adapted from (Wu and Xiong, 2014)]. We then explored the effect of mixing historical and contemporaneous controls in select mixtures into a single control arm, noting a very slight improvement in power to detect improvements in survival. Overall, a control arm sample size of 90 patients, in historical/contemporaneous control mixtures of 90+0, 80+10, 70+20, and 60+30 all have at least 80% power to detect improvements in survival between 6 and 8 months.

TABLE 10: POWER TO DETECT M MONTHS IMPROVEMENT IN MEDIAN OVERALL SURVIVAL UNDER SELECTED SCENARIOS

Accrual rate (N/mo)	Accrual period (mos)	Follow-up period (mos)	Trial N	Hx Ctl+ Contemp N	Weibull shape k	Power to detect M months improvement in median OS at one-sided $\alpha=0.05$ using the log-rank test				
						M = 4	5	6	7	8
2.5	36	24	90	50+ 0	2.0	0.525	0.667	0.782	0.866	0.922
2.5	36	24	90	60+ 0	2.0	0.565	0.711	0.823	0.899	0.946
2.5	36	24	90	70+ 0	2.0	0.598	0.745	0.853	0.922	0.962
2.5	36	24	90	80+ 0	2.0	0.626	0.773	0.876	0.938	0.972

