11.4 Protocol Amendment History

The table below is intended to capture changes of IRB-approved versions of the protocol, including a description of the change and rationale. A Summary of Changes table for the current amendment is located in the Protocol Title Page.

Version	Date	Section	Description of Change	Brief Rationale
1.1	5 April 2019	Title Page	Addition of NCT and IDE numbers	Updates flowing from IDE approval
1.1	5 April 2019	1.1	Clarification/Correction of enrollment vs. participant timelines	Response to FDA initial review question
1.1	5 April 2019	2.1.1.1	Addition of generalizability of results section	Clarification of potential benefits to the Medicare population from study results
1.1	5 April 2019	10.1.11	Revision of Publication Policy	Updated to reflect the current study contract
1.1	5 April 2019	1.3, 5.5.1, 6.3.1, 8.1.4	Consistent description of acceptable tissue sample types	FFPE, pathology slides, or frozen samples are acceptable for onsite tissue verification; only FFPE and pathology slides may be shipped
2.1	16 Dec 2019	1.1, 9, 10, 10.3, 11.1.1	Addition of Control Cohort	Methodological improvement in the historical control for this study
2.1	16 Dec 2019	4.1.3, 5.1, 5.5	Removal of Inclusion criteria regarding 1p/19q and/or ATRX	Update of WHO Classification of Grade II and III criteria for gliomas
2.1	16 Dec 2019	5.1	Addition of Inclusion criteria	Clarify patients appropriate for Optune
2.1	16 Dec 2019	1.1, 10.3	Removal of Stupp Protocol specification	Avoid any specific Gy requirement assumption analogous with Stupp
2.1	16 Dec 2019	6.1.1.3	Addition of RANO clarification regarding non-enhancing disease	Clarification of criteria for non-enhancing disease via FLAIR
2.1	16 Dec 2019	10.2.1	Addition of stratification by extent of resection	Implementation of FDA suggestion
2.1	16 Dec 2019	1.3, 5.1, 5.4, 6.1, 6.2, 6.3, 8.1.2	Minor Typographical Updates	Clarification
2.1	16 Dec 2019	11.1.6, 11.1.7	Update DSMB audit frequency	Updated to reflect current study approved risk level (moderate) and related annual DSMB audit frequency
2.1	16 Dec 2019	Sections not applicable to this protocol (and therefore intentionally left blank)	Removed to avoid confusion	Implementation of SRMC suggestion for readability.

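### The only committed OS and PFS test between non-randomised arms is an unadjusted log-rank, with stratification left optional, so prognostic imbalance goes uncorrected

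*Combined protocol and SAP*

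**What the plan says.** Section 10.2.1 gives the analysis of OS and PFS in one sentence: "We will compare OS and progression-free survival (PFS) between historical control and experimental treatment arms using the log-rank test". Its closing sentence is the only covariate language that can apply to those endpoints: "We may stratify the patients by MGMT methylation status, extent of resection, or a combination of the two". It gives no trigger, date, resection categories or primary version.

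Confounding is mentioned once, for the correlative mutation-burden comparison, and again as an option: "We may perform the same comparison within a linear regression framework if the need arises to adjust for any potential confounders". No Cox model, weighting or matching is planned for OS. Age, KPS and WHO grade do not appear in the OS plan.

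The screening list in 5.5.1 includes "MGMT methylation status (if feasible, required for stratification".

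On the comparator, 10.1 says that "the control arm will consist of both historical and contemporaneous control patients", and 10.2 describes "mixing historical and contemporaneous controls in select mixtures into a single control arm". Sections 9 and 10.1 explain how controls arise: historical controls by chart review, and contemporaneous controls because the patient declines the device for non-medical reasons. Section 9.1 acknowledges the stakes: "Identification of a homogeneous historical cohort for comparing the investigational device data to historical data is of critical importance".

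**The concern.** A log-rank p-value speaks to the device only if the arms would have had the same survival without it. Here arm membership depends on calendar period and patient preference, and nothing in the committed analysis allows for differences that follow from either.

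The shared sites, 2016 start, common genotype, KPS of at least 70 and absence of early progression narrow the room for imbalance. They still allow the arms to differ in age, grade II versus III, gross total resection versus biopsy, MGMT status, and KPS within 70 to 100.

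This is the sole primary test, and a correction is credible only if it is fixed before outcomes are compared.

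**Working it through.** **Inputs from 10.1 and 10.2.** 90 versus 90 patients; control median 22 months; Weibull shape k = 2.0 (1.8 as alternative); 36 months of accrual plus 24 of follow-up, so device patients are followed for 24 to 60 months; one-sided 0.05. Assumed: controls are also followed uniformly for 24 to 60 months (the documents give only a maximum of 60).

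**1. The plan's own figure.** For a 6-month gain, HR = (22/28)² = 0.617 and |ln HR| = 0.482. The chance of death is 1 − exp[−ln 2 × HR × (t/22)²] averaged over t = 24 to 60 (HR = 1 for controls). This gives 0.871 for controls and 0.751 for device patients, so deaths = 90 × (0.871 + 0.751) = 146. Power = Φ(√(146/4) × 0.482 − 1.645) = Φ(1.27) = 0.898, against 0.894 in Table 10 (90+0, k = 2.0). For gains of 4 to 8 months the same method gives 0.655, 0.801, 0.898, 0.953 and 0.980, against 0.649, 0.796, 0.894, 0.950 and 0.979. Table 10 is sound, but it presumes exchangeable arms.

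**2. False benefit with no device effect.** Assume one favourable binary factor with hazard ratio h, prevalence p_C = 0.40 in controls and p_E in the device arm. The spurious log hazard ratio is approximately b = ln{[1 − (1 − h)p_E] / [1 − (1 − h)p_C]}. The one-sided error is Φ(−1.645 − b√(D/4)), with D about 155 deaths under the null and √(155/4) = 6.225.

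Example: h = 0.5, p_E = 0.50. b = ln(0.75/0.80) = −0.0645, and Φ(−1.645 + 0.402) = 0.107.

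| h | Device arm, points | b | Formula | Simulated, unadjusted |
|---|---|---|---|---|
| 0.5 | +10 | −0.0645 | 0.107 | 0.107 |
| 0.5 | +20 | −0.1335 | 0.208 | 0.198 |
| 0.5 | −10 | +0.0606 | 0.022 | 0.020 |
| 0.5 | −20 | +0.1178 | 0.009 | 0.008 |
| 0.7 | +10 | −0.0347 | 0.077 | 0.078 |
| 0.7 | +20 | −0.0706 | 0.114 | 0.112 |
| 0.7 | −10 | +0.0335 | 0.032 | 0.031 |
| 0.7 | −20 | +0.0660 | 0.020 | 0.020 |

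Each simulated value comes from 20,000 trials. Repeat runs agreed within simulation error, apart from 0.005 to 0.008 in the fourth row. A log-rank stratified on the factor stayed between 0.046 and 0.054 throughout. Doubling the error to 0.10 takes an imbalance of about 9 points at h = 0.5, 16 to 17 at 0.7 and 27 at 0.8.

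**3. Hidden benefit.** With a true 6-month gain and h = 0.5, simulated unadjusted power is about 0.84 to 0.86 when the factor is balanced. It falls to about 0.74 with 10 points against the device and about 0.60 with 20. The stratified test holds about 0.88 to 0.89.

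**4. The two candidate corrections.** Let MGMT, resection and one further factor each have a hazard ratio of 0.7 and each lean 10 points towards the device. The error is then 0.145 unadjusted, 0.080 for a log-rank stratified by resection and MGMT (nine strata), and 0.060 for a Cox model with all the factors. If only MGMT and resection are shifted, the stratified log-rank gives 0.052 and Cox 0.056.

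**5. Power cost.** This is for a 6-month gain with balanced arms and no prognostic factor. The Cox figures use a slightly tightened critical value (−1.70) that brings its size back to about 0.05.

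| k | Unadjusted | Nine strata | Cox |
|---|---|---|---|
| 2.0 | 0.897 | 0.865 | 0.879 |
| 1.8 | 0.829 | 0.794 | 0.810 |

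If all three factors are prognostic and balanced, the figures at k = 2.0 are 0.856, 0.830 and 0.864.

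**The case against.** The best defence is that the illustration rests on chosen inputs. That is correct: the documents supply no prevalence, prognostic hazard ratio or expected imbalance. A single factor with hazard ratio 0.7 and a 10-point imbalance moves the error only to about 0.08, and the 0.145 case needs three factors leaning the same way. The figures show sensitivity and do not predict this trial's error. The gap does not depend on them, because the committed test corrects for no imbalance of any size.

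Preferring Cox to a stratified log-rank is also partly taste. The size advantage of Cox comes from a third prognostic factor, and nothing in the documents shows that grade is strongly prognostic within this genotype; section 2.1.1.1 leans the other way. Either analysis would close the gap.

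Three stronger readings are tempting and are not supported:

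- **The documents contradict themselves on stratification.** Section 5.5.1 fits poorly with the optional wording in 10.2.1. But it is a checklist entry qualified by feasibility, and can mean that the data are needed if stratification is done.
- **An agreed change was not carried through.** The amendment history in 11.4 records "Addition of stratification by extent of resection" as an FDA suggestion. Section 10.2.1 does contain extent of resection, and the log does not say that stratification was to be mandatory. The two agree.
- **The strata will be picked after outcomes are seen.** If so, the best of four log-ranks (none, MGMT, resection, both) would have an error of about 0.07 to 0.09 even with balanced arms. But the sentence is equally consistent with supportive analyses only. It leaves the choice open; it does not announce it.

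**Conclusion.** The concern holds. As written, the primary OS test and the PFS test compare non-randomised arms with no committed correction for prognostic imbalance, although the main factors are largely collected in both arms.

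Under the stated assumptions (one binary factor, 40% in controls, nominal one-sided 0.05), the error is about 0.11 or 0.02 for 10 points and 0.20 or below 0.01 for 20 points at a hazard ratio of 0.5. At 0.7 it is about 0.08 or 0.03, and 0.11 or 0.02. The direction of any real imbalance is unknown, so the bias could favour or penalise the device. The power table is not in question.

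Two neighbouring matters need their own treatment and are not part of this point: 10.2.1 names only historical controls, and 10.1 and 10.3 rely on first-tier criteria that are never defined.

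**What to change.** Before any OS comparison, replace the optional stratification sentence in 10.2.1 with one named primary analysis of the interventional arm against the pooled historical plus contemporaneous control arm. Choose one:

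- a Cox model adjusted for age, KPS, WHO grade, extent of resection (GTR, partial, biopsy) and MGMT; or
- a log-rank that will be stratified by extent of resection and MGMT.

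With either:

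- Code MGMT as methylated, unmethylated (including indeterminate, as 11.2.2 and 11.2.2.1 already say), or not feasible as its own category. The third category matters. In a simulation with balanced arms and MGMT missing in 30% of controls and 10% of device patients, coding missing as unmethylated gave a stratified-test size of 0.025, against 0.050 with a separate category (hazard ratio 0.5 assumed for MGMT and for GTR versus biopsy).
- Take control KPS from the chart value nearest the start of adjuvant temozolomide; 9.5 and 11.2.2.1 give no time point.
- Use the same method for PFS, and keep the unadjusted log-rank as supportive.

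**Cost.** SAP text and possibly some chart abstraction for KPS. Demographics, pathology, extent of operation and MGMT reports are already required (5.5.1, 9.5, 11.2.2, 11.2.2.1). If the factors turn out not to be prognostic, power falls by about 2 points for Cox and about 3 for the stratified log-rank, which at k = 1.8 is just under 80% for a 6-month gain. Cox size is slightly above nominal, about 0.055 to 0.060. That can be checked by simulation with the final coding, and no special critical value need be fixed now. The stratified log-rank leaves age, KPS and grade uncorrected.

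Neither option removes residual confounding, including that from differences in control eligibility and time origin. Table 2 counts OS from Study Day 0 and states no equivalent for controls, and control criterion G in 9.2 requires adjuvant temozolomide to have been completed.

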Gliomas are generally considered to have low mutation burden compared to ICI-sensitive tumors [65]. The combination of radiotherapy and temozolomide, an alkylating agent, has been suggested to increase mutation burden in gliomas [66], however it remains unclear if this modest increase was sufficient to improve response to ICIs. Early clinical experience of ICIs in recurrent malignant gliomas showed minimal efficacy [67, 68]. However high-grade gliomas with a hypermutant phenotype, such as in patients with germline biallelic mismatch repair deficiency, demonstrated significant and durable response to ICIs [69], indicating that very high mutation burden may improve gliomas' response to ICIs. Recent study in an animal model of lung cancer suggested that TTFIELDS targeted DNA repair mechanisms [70], which potentially could greatly enhance mutation burden in treated tumors over time. These results raise the possibility that the addition of TTFIELDS to chemoradiotherapy in glioma treatment may be sufficient at increasing mutation burden above the threshold of necessary for meaningful and durable response to ICIs. Although immunotherapy and ICIs are not the focus of the current protocol, we propose to determine whether TTFIELDS can indeed increase mutation burden since the results will have significant impact for future trials and treatment development for gliomas in general. Tumor mutational burden will be assessed by standard clinical DNA sequencing on pre-treatment (i.e. at initial surgery) and post-treatment (i.e. first radiographic recurrence while receiving adjuvant temozolomide and TTFIELDS and any subsequent recurrences, where available from standard care procedures) tumor specimens. These results will be compared to historical and concurrent data available on patients with malignant gliomas similarly treated at participating institutions with radiation and temozolomide only and without TTFIELDS. Both microsatellite status and mutation burden, expressed as number of mutations per Mb, will be obtained and compared between the 2 groups.

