
 • To determine whether the addition of TTFIELDS to adjuvant temozolomide significantly increase mutation burden, compared to historical and contemporaneous controls. • To determine whether TTFIELDS increases immune cell infiltration. • To determine whether TTFIELDS induces immunogenic cell death in tumor. 	
 • Mutation burden before and after TTFIELDS, compared to historical and contemporaneous controls • Immune cell infiltration before and after TTFIELDS, compared to historical and contemporaneous controls • Immunogenic cell death marker before and after TTFIELDS, compared to historical and contemporaneous controls • Computer modeling of electric field and energy deposition 	To add key immunological and mutational information to the information about these specific tumors.

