6.3 Correlative Studies

6.3.1 Tumor Tissue Specimens

6.3.1.1 Collection of specimens

Formalin fixed and paraffin embedded (FFPE) samples will be obtained from pathology or research tissue banks from primary tumors and first recurrent tumors, when available. One FFPE tissue block or fifteen slides of 20 µm thick section will be required for analysis. At least 20 pairs of primary tumors and first recurrent tumors from patients treated only with RT and concurrent temozolomide followed by adjuvant temozolomide, and not with TTFields or any other modalities (drug, radiation or device), are needed.

The Coordinating Center will obtain at least 20 historical paired samples from patients with the same tumor type or GBM before and after being treated with temozolomide and RT, but not with TTFields, over the last 5 years at the same participating institutions.

Sequencing analyses will be obtained by standard of care sequencing (immunohistochemistry or next-generation sequencing), from which mutation burden data will be obtained. Mutation burden will be expressed as number of mutations per Mb and will be extracted from sequencing reports for primary tumors and first recurrent tumors, where available.

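### The mutation-burden t test in Section 10.2.1 names no analysis variable and fixes no baseline adjustment; on raw means it loses precision, and GBM control pairs could confound it

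*Combined protocol and SAP*

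**What the plan says.** Table 2 in Section 3 of the combined protocol and SAP lists as an exploratory endpoint "Mutation burden before and after TTFIELDS, compared to historical and contemporaneous controls".

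Section 6.3.1.1 collects tissue for it: "At least 20 pairs of primary tumors and first recurrent tumors from patients treated only with RT and concurrent temozolomide"; these patients went on to adjuvant temozolomide and had no TTFields. For the historical part it asks for "at least 20 historical paired samples from patients with the same tumor type or GBM before and after being treated", again without TTFields. Burden is read from sequencing reports on primary and first recurrent tumours, where available, as mutations per Mb. The number of TTFields pairs is not stated. Section 9.5 makes tissue optional for control-cohort patients, and Section 10.3 defines the interventional population as Grade II or III astrocytoma.

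The analysis in Section 10.2.1 is "we will use the independent-sample t test to compare mean mutation burden between patient samples treated with RT+temozolomide or RT+temozolomide+TTFields". The next sentence reads "We may perform the same comparison within a linear regression framework if the need arises to adjust for any potential confounders"; it names no covariate and no trigger. The optional strata are given by "We may stratify the patients by MGMT methylation status, extent of resection, or a combination of the two". Tumour type appears in neither sentence. No transformation, alpha, effect size or power is given for this endpoint.

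**The concern.** Three things are left open.

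1. **Analysis variable.** The endpoint is before-and-after and pairs are collected, but the test sentence does not say whether the recurrent value, the change, or all samples together are compared.
2. **Scale and baseline.** Mutations per Mb cannot be negative and may be right-skewed. A t test on raw means is sensitive to a few high values, and if only recurrent values are compared it makes no use of the paired primary value.
3. **Tumour type.** Historical control pairs may be GBM with no cap on their share, and optional control-cohort tissue means same-type pairs are not assured. No TTFields patient has a GBM diagnosis under Section 10.3. If burden differs by tumour type, a difference in means mixes that with treatment, in a direction the documents do not allow us to predict.

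At stake is an exploratory result that Section 2.1.2.6.1 expects to inform future trials. It could miss a real increase, or report or hide one because of tumour type.

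**Working it through.** The plan states no power or detectable difference for mutation burden (Table 10 covers OS only), so there is no figure to reproduce. The following is illustrative.

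**Inputs.** From the documents: at least 20 control pairs (Section 6.3.1.1). Assumed: m = 20 TTFields pairs, two-sided alpha 0.05, log-scale SD 0.6, a 1.6-fold effect, and primary-recurrent correlation ρ of 0.2 to 0.8.

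**Step 1: what the baseline value is worth.** Relative to comparing recurrent values only, the variance is 2(1−ρ) for a change score and 1−ρ² for ANCOVA on the primary value. The difference detectable with 80% power is (1.960 + 0.842) × √(1/20 + 1/20) = 0.89 SD for recurrent values only, and scales with the square root of the relative variance.

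| ρ | Change: variance | Change: detectable | ANCOVA: variance | ANCOVA: detectable |
|---|---|---|---|---|
| 0.2 | 1.60 | 1.12 SD | 0.96 | 0.87 SD |
| 0.5 | 1.00 | 0.89 SD | 0.75 | 0.77 SD |
| 0.7 | 0.60 | 0.69 SD | 0.51 | 0.63 SD |
| 0.8 | 0.40 | 0.56 SD | 0.36 | 0.53 SD |

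Change scores help only when ρ exceeds 0.5. ANCOVA gains at any non-zero ρ, but by only 4% of variance at ρ = 0.2.

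**Step 2: power without GBM controls.** The log effect is ln 1.6 = 0.470. For ANCOVA at ρ = 0.5 the standard error is 0.6 × √0.75 × √(1/20 + 1/20) = 0.164. So z = 0.470/0.164 = 2.86 and normal-approximation power is Φ(2.86 − 1.96) = 0.82. Simulation, which allows for the small sample, gives somewhat less:

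| ρ | Raw t test, recurrent values | Log-scale ANCOVA |
|---|---|---|
| 0.2 | about 0.61 | 0.68 |
| 0.5 | about 0.61 | 0.77 |
| 0.7 | about 0.61 | 0.91 |

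At ρ = 0.2 a t test on log values already reaches about 0.67, so nearly all the gain there comes from the log scale. If 10% of recurrences in both groups were hypermutated with a tenfold rise (both assumed), power would be about 0.11 for the raw t test. It would be about 0.35 to 0.40 on the log scale, with or without the baseline value.

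**Step 3: tumour type, with no TTFields effect.** Bias in SD units is f × d, where f is the GBM share of controls and d the tumour-type difference. The chance of a false positive is the normal tail beyond 1.96 after a shift of f × d/√(1/20 + 1/20).

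- f = 0.5, d = 0.5: shift 0.25/0.316 = 0.79, rate 0.12 (simulated raw t test about 0.10).
- f = 1, d = 0.5: shift 0.5/0.316 = 1.58, rate 0.35 (simulated about 0.30).
- f = 0.25, d = 0.25: rate 0.05.

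Baseline adjustment alone lowers the two simulated rates to about 0.07 and 0.14 at ρ = 0.5. It does not remove the bias.

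**Step 4: the price of a tumour-type term.** Because no TTFields patient has GBM, the adjusted treatment contrast rests on the same-type controls only. With ρ = 0.5:

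- 10 of 20 controls GBM: SE = 0.520 × √(1/20 + 1/10) = 0.201, z = 2.34, approximate power 0.65 (simulated about 0.61).
- 15 of 20 GBM: SE = 0.520 × √(1/20 + 1/5) = 0.260, z = 1.81, approximate power 0.44 (simulated about 0.40).
- All GBM: group and tumour type coincide, and the effect cannot be estimated.

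**The case against.** The groups are different patients, so an independent-sample test is the right type and a paired t test could not replace it. The before-and-after endpoint is compatible with a t test on change, which would use the baseline; a tumour-type difference that is the same in both samples on the analysed scale would then cancel. The plan also allows regression for confounders, and Section 2.1.1.1 argues that these tumours behave as molecular GBM. The endpoint is exploratory, with no decision rule.

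Much of this stands. A reader might infer that the unpaired test is an error, or that the plan certainly ignores the baseline; the text supports neither, since it does not name the variable. A reader might also infer that tumour type will confound the result. That needs GBM pairs to be used and burden to differ by type, and the documents quantify neither. Nor does the mention of "high-grade gliomas with a hypermutant phenotype" in Section 2.1.2.6.1 support a hypermutation rate here: its example is germline mismatch repair deficiency, and the same section calls the rise after radiotherapy and temozolomide modest.

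What does not stand is that the plan already deals with the matter. The regression is discretionary, without a covariate list or trigger. The molecular-GBM argument concerns prognosis and management, and does not show equal mutation burden.

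**Conclusion.** The point holds as a low-severity improvement to an exploratory analysis. The plan should name its analysis variable, and a log-scale model adjusted for the primary tumour is a better default than a t test on raw means. Under the stated assumptions, power rises from about 0.61 to between 0.68 and 0.91, depending on the correlation. The gain is small at low correlation, where it comes mainly from the log scale.

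Confounding by tumour type is a risk left open. With a 0.5 SD difference by type, the raw t test's false-positive rate would be about 10% with half the controls GBM and about 30% with all GBM. With a small GBM share and a small difference it would stay near 5%.

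SD, correlation, effect, hypermutation share, GBM share and TTFields pair count are all assumptions. It would also go too far to call the whole remedy free, because proper handling of GBM pairs reduces the effective number of controls. The primary OS analysis is unaffected.

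**What to change.** In Section 10.2.1:

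- State the analysis variable, and make the planned analysis a linear model of log(recurrent burden) on treatment group and log(paired primary burden), with a stated rule for zero values.
- Use control pairs of the study tumour type for the main treatment contrast.
- Report GBM control pairs separately, or include them with a tumour-type term only when enough same-type control pairs exist.
- Add a rank-based check.

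In Section 6.3.1.1, say how many of the 20 or more control pairs must be of the study tumour type.

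The log scale and baseline adjustment need no new data, since the primary value is already sought. Handling GBM controls properly does have a cost: either more same-type pairs must be found, or lower power accepted (about 0.61 and 0.40 with 10 and 15 of 20 controls GBM, at correlation 0.5).
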